Blood samples for the measurement of adalimumab concentrations will be collected at Baseline, Weeks 2, 4, 8, 12, 26, 34 and 52/Premature Discontinuation Visits and at Unscheduled Visits requiring dose change. Blood samples for measurement of

anti-adalimumab antibodies (AAAs) will be collected at Baseline, Weeks 4, 8, 26 and 52/Premature Discontinuation Visits and at Unscheduled Visits requiring dose change.

Blood samples for measurement of human anti-chimeric antibody (HACA) to infliximab as well as infliximab drug levels will also be collected at Week 0.

Subjects are allowed to be treated with stable doses of UC-related concomitant medications during the study, with the following exceptions and requirements:

- At or after Week 4, subjects taking corticosteroid therapy at Baseline may have their corticosteroid therapy tapered based on the investigator's discretion. A proposed tapering schedule is specified in Section 5.3.1.1.
- From Week 4 to Week 12, if the subject should experience an increase in symptoms after corticosteroid was tapered, the subject may have their corticosteroid dose increased back up to the corticosteroid dose at Baseline. This increase must be discussed with and approved by the Medical Monitor prior to any changes in these treatments.
- Subjects who experience disease flare at or after Week 12 are allowed to change their dose or initiate treatment with corticosteroids, immunosuppressants or 5-ASA; these increases must be discussed with and approved by the Medical Monitor prior to any changes in these treatments.
- Immunosuppressant doses may be decreased or terminated in the event of moderate-to-severe treatment-related toxicities (e.g., leukopenia or elevated liver enzyme) considered moderate to severe in the opinion of the investigator.
- Immunosuppressant therapy may be discontinued at or after Week 12 at the investigator's discretion.

Treatment of Subjects with a Disease Flare During the Study

Criteria for Disease Flare are as follows:

- Subjects with a Week 8 PMS of 0 to 2 who present with a PMS at least 3 points greater than their Week 8 score.

- Subjects with a Week 8 PMS of 3 to 4 who present with a PMS at least 2 points greater than their Week 8 score.
- Subjects with a Week 8 PMS of 5 to 6 who present with a PMS at least 1 point greater than their Week 8 score.

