Subjects will be expected to remain on blinded therapy throughout the 44-week maintenance period. However, subjects with a disease flare may be re-randomized to receive the following blinded-treatment at or after Week 12, [Figure 4](#).

- Subjects who are randomized to standard maintenance dose (0.6 mg/kg eow [maximum of 40 mg eow]) will be re-randomized to receive either adalimumab re-induction dose (2.4 mg/kg [maximum of 160 mg]) or adalimumab (0.6 mg/kg [maximum of 40 mg]) at the visit. Afterwards, all subjects will resume receiving the standard dose (0.6 mg/kg [maximum of 40 mg] eow) within the original dosing schedule.
- Subjects who are randomized to high maintenance dose (0.6 mg/kg ew [maximum of 40 mg ew]) will be re-randomized to receive either adalimumab re-induction dose (2.4 mg/kg [maximum of 160 mg]) or adalimumab (0.6 mg/kg [maximum of 40 mg]) at the visit. The following week, all subjects will resume receiving the high dose (0.6 mg/kg [maximum of 40 mg] ew).
- Subjects who were randomized to placebo prior to Amendment 4 will be re-randomized to receive either adalimumab re-induction dose (2.4 mg/kg [maximum of 160 mg]) or to receive adalimumab (0.6 mg/kg [maximum of 40 mg]) at the visit. Afterwards, all subjects will receive the standard dose (0.6 mg/kg [maximum of 40 mg] eow) within the original dosing schedule.

If a subject continues to meet the definition of disease flare (2nd time) following at least a 4-week course of blinded therapy since the subject has been re-randomized for the disease flare, they may be switched to open-label adalimumab every week at the dose 0.6 mg/kg [maximum of 40 mg]. *(If a subject was re-randomized at Week 12 (to receive either re-induction dose (2.4 mg/kg [maximum of 160 mg]) or to receive adalimumab (0.6 mg/kg [maximum of 40 mg])), then the earliest that subject could be evaluated to determine if*

they meet the criteria for disease flare for switch to OL (0.6 mg/kg [maximum of 40 mg]) weekly dosing is at Week 16.

If a subject continues to meet the definition of disease flare (3rd time) following a 4-week course of open-label adalimumab every week at the dose 0.6 mg/kg [maximum of 40 mg], they may be switched to receive adalimumab open-label 40 mg ew (maximum dose, not weight based).

Subjects with persistent disease flare while on adalimumab 40 mg ew (max dose) may be withdrawn from the study at the investigator's discretion.

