5.2.3.2 Concomitant Therapy

Subjects may continue their doses of azathioprine, 6-MP or MTX provided they are on these medications for at least 28 days prior to Baseline and that doses have been stable for at least 28 days prior to Baseline. Doses of these concomitant medications (azathioprine, 6-MP or MTX) must remain stable for the first 12 weeks of participation, except in the event of treatment-related toxicities (e.g., leukopenia or elevated liver enzymes) considered moderate to severe in the opinion of the investigator. Immunosuppressant

dose (azathioprine and 6-MP or MTX) can be discontinued starting at Week 12 per investigator's discretion. Subjects who experience disease flare at or after Week 12 are allowed to change their dose or initiate treatment with corticosteroids, immunosuppressants or 5-ASA; these increases must be discussed with and approved by the Medical Monitor prior to any changes in these treatments.

Subjects may continue doses of aminosalicylates provided they are on these medications for at least 14 days prior to Baseline and that doses have been stable for at least 14 days prior to Baseline. Oral antibiotics are permitted prior to Baseline and subjects may continue these medications provided that they were prescribed for ulcerative colitis but not for treatment of an infection. Corticosteroids are permitted if the subject has been on stable doses prior to Baseline as outlined in inclusion criterion 3 in Section 5.2.1. Subjects are not allowed to change the corticosteroid dose during the first 4 weeks of the study. At or after Week 4, subjects who are taking corticosteroid therapy at Baseline may have their corticosteroid therapy tapered off based on the investigator's discretion.

A proposed schedule to taper corticosteroid dose starts with a weekly decrease by 5 mg/day prednisone (or equivalent) for doses > 10 mg/day of prednisone (or equivalent) until a 10 mg/day (or equivalent) dose is reached, then a weekly decrease by 2.5 mg/day (or equivalent) until discontinuation.

A proposed schedule to taper budesonide dose starts with a weekly decrease by 3 mg/day until discontinuation.

From Week 4 to Week 12, if the subject should experience an increase in symptoms after corticosteroid was tapered, the subject may have their corticosteroid dose increased back up to the corticosteroid dose at Baseline. This increase must be discussed with and approved by the Medical Monitor before.

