Subjects ≥ 9 years old at Baseline will complete an IMPACT III questionnaire at Baseline, Week 8, Week 26 and Week 52/Premature Discontinuation Visit.

WPAI Questionnaire

Work Productivity and Activity Impairment Questionnaire (WPAI) will be completed at every visit except the Unscheduled Visit ([Appendix F](#)).

The subject's parent or legal guardian will complete the WPAI. The questionnaire will not be completed if the subject's parents or legal guardian do/does not take care of the subject anymore.

Corticosteroid Therapy

At or after Week 4, subjects taking corticosteroid therapy at Baseline may have their corticosteroid therapy tapered based on the investigator's discretion. Following is the proposed tapering schedule:

	Daily Dose	Rate of Tapering Daily Dose
Prednisone (or equivalent)	> 10 mg	5 mg/week
	≤ 10 mg	2.5 mg/week
Budesonide	≤ 9 mg	3 mg/week

From Week 4 to Week 12, if the subject should experience an increase in symptoms after corticosteroid was tapered, the subject may have their corticosteroid dose increased back up to the corticosteroid dose at Baseline. This increase must be discussed with and approved by the Medical Monitor prior to any changes in these treatments.

At or after Week 12, if the subjects should experience disease flare, the subjects may have their corticosteroid dose initiated, reinitiated or increased above the corticosteroid dose at Baseline. These initiations, reinitiations or increases must be discussed with and approved by the Medical Monitor prior to any changes in these treatments.

Immunosuppressant Therapy

At and after Week 12, subjects who are on immunosuppressant (azathioprine, 6-MP or MTX) and have experienced a significant improvement in their clinical response are permitted to discontinue their dose according to the investigator's discretion.

At or after Week 12, if the subject should experience a loss of clinical response the subject may have their immunosuppressant dose increased, initiated or reinitiated with immunosuppressants. These increases, initiations or re-initiations must be discussed with and approved by the Medical Monitor prior to any changes in these treatments.

Subject Diary/Dosing Log

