8.1.4 Statistical Analyses of Efficacy

The efficacy analysis will be performed in the ITT-E population for the Week 8 efficacy endpoints and in the mITT population for the Week 52 efficacy endpoints. Non-responder imputation (NRI) will be used to impute missing values for binary efficacy endpoints. Subjects who do not complete the induction period or who receive rescue therapy during the maintenance period will be considered as failures from that time point forward. Both LOCF and observed case analyses will be performed for continuous efficacy endpoints.

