Non-responder Imputation (NRI): The NRI approach is used for all binary efficacy variables. These variables can take values of 'Response' (i.e., response, remission or mucosal healing) or 'Non-response' (i.e., non-response, non-remission or no mucosal healing) or may be missing for any reason including discontinuation from study. According to the NRI method all missing values will be considered as 'Non-Response'. Subjects re-randomized due to disease flare will be considered as 'Non-Responders' at and after their 1st re-randomization. The confirmatory efficacy analyses will use NRI approach to impute the missing values.

Additionally, only for sensitivity analyses on the mITT population, a **modified NRI** (**mNRI**) approach to impute the missing values will be used. For mNRI method, subjects re randomized due to disease flare will be considered as 'Non-Responders' at and after the switch to the open-label therapy (2nd disease flare).

Last Observation Carried Forward (LOCF): For categorical and continuous efficacy variables the following rules will be used for LOCF approach:

- Baseline and pre-baseline values will not be used to impute the missing post-baseline values, and
- Missing values after baseline will be imputed using the last non-missing values
 after baseline and prior to the missing value. This includes values from
 unscheduled visits and visits where the measurement was not planned to be
 collected per protocol.
- For subjects who were re-randomized due to disease flare, the last non-missing value before or at the re-randomization after 1st disease flare will be carried forward.

[figure not shown]
Unless otherwise noted, for composite scores which consist of several component subscores, components will be imputed first and the composite score will be calculated based on imputed component subscores. Only if composite score still can't be calculated after imputing component subscores, then the previous composite score will be carried forward. The LOCF analysis will only be performed as sensitivity analysis.

Observed Cases (OC): Observed case analysis will be performed on data until 1st re-randomization of subjects with a disease flare. The following rule will be used: missing values will not be used for the observed case analysis. The OC analysis will only be performed as sensitivity analysis.

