9.1 Study Drug Exposure

Induction study drug exposure will be summarized for ITT, ITT-E and safety population by treatment groups defined in Section 5.1. The study drug exposure during induction period does not include the dose received at Week 8. The duration of exposure during induction period will be calculated as follows:

Duration of induction-exposure = last induction dose date - first induction dose date + (max.*) 14 days

*cutting before first dose of study drug in the maintenance period.

Maintenance study drug exposure will be summarized for mITT, mITT-E, RR and safety population (restricted to subjects who received at least one dose of the study drug during maintenance phase). Of note, patients in this study don't receive study drug at Week 52, unless they roll over into Study M10-870, then this will be their first dose of study drug in Study M10-870 (and will be documented in Study M10-870, not Study M11-290). The duration of exposure during maintenance will be calculated as follows:

Duration of maintenance-exposure = last maintenance dose date (prior to potential re-randomization due to 1st disease flare) – first maintenance dose date + (max.*) 14 days

*cutting before first dose of study drug after re-randomization due to 1st disease flare, if applicable, or the first dose of study drug in Study M10-870, if applicable.

[figure not shown]
ADA exposure after re-randomization due to 1st disease flare for the RR population will be calculated as follows:

Duration of ADA exposure after 1st disease flare = last adalimumab dose date in the study after re-randomization due to 1st disease flare – first dose date of adalimumab after re-randomization due to 1st disease flare + (max.*) 14 days

*cutting before first dose of study drug in Study M10-870, if applicable

The overall adalimumab exposure (regardless of double-blind or open-label treatment or if it was rescue therapy after disease flare) will be summarized for the safety population. The duration of overall exposure will be calculated as follows:

- Subjects who are randomized to placebo at Week 8 and who have not been re-randomized due to a disease flare:
 - Overall ADA exposure = Duration of induction-exposure
- Subjects who are randomized to placebo at Week 8 and are re-randomized due to at least one disease flare during maintenance:

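### SAP 6.0 fails a flaring child on co-primary 2 only after re-randomization, so Week 52 remission reached with added corticosteroid, immunosuppressant or 5-ASA can count as an adalimumab success

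*SAP*

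**What the plan says.** **Confirmatory rule.** SAP Section 6.0 makes non-responder imputation (NRI) the method for the confirmatory analyses. Missing values are non-response. The only other trigger is: "Subjects re-randomized due to disease flare will be considered as 'Non-Responders' at and after their 1st re-randomization".

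**Protocol rule.** Section 8.1.4, repeated in the synopsis, fails subjects "who receive rescue therapy during the maintenance period will be considered as failures from that time point forward". Neither document defines rescue therapy.

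**What a flaring child may receive.** Two routes are open from Week 12.
- Study drug: "subjects with a disease flare may be re-randomized to receive the following blinded-treatment at or after Week 12" (Protocol Section 5.1). Section 8.3 also says may.
- Other UC drugs: "Subjects who experience disease flare at or after Week 12 are allowed to change their dose or initiate treatment with corticosteroids, immunosuppressants or 5-ASA". Section 5.2.3.2 repeats this. For corticosteroids, Section 5.3.1.1 says: "if the subjects should experience disease flare, the subjects may have their corticosteroid dose initiated, reinitiated or increased above the corticosteroid dose at Baseline". Medical Monitor approval is required. None of these sections makes the added drug depend on re-randomization.

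**The concern.** The second co-primary endpoint is Mayo remission at Week 52 in Week 8 responders, tested one-sample against a fixed external placebo rate of 18.37%. There is no concurrent control arm in that test to absorb the effect of added treatment. Consider a child who flares in maintenance, starts prednisone or azathioprine, is not re-randomized, and is in remission at Week 52. Under the SAP as written, that remission is credited to adalimumab. A child with the same flare who is re-randomized is a failure, whatever the Week 52 score. The difference rests on an optional step, and the SAP does not say that this is intended.

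**Working it through.** **1. Does any planned analysis fail this child?** The child flares after Week 12, receives an added UC drug, is not re-randomized, has complete data and is in Mayo remission at Week 52.

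| Analysis | What overrides the observed outcome | Fails this child? |
|---|---|---|
| NRI (confirmatory) | missing data; first re-randomization | No |
| mNRI | switch to open-label therapy at second flare | No |
| LOCF | values frozen at first re-randomization | No |
| OC | data used only up to first re-randomization | No |
| MI | *rescue medication*, undefined; discontinuation for lack of efficacy | Cannot be told |
| Per protocol (NRI) | major deviations excluded | No: the added drug is permitted, so not in itself a deviation |
| Ranked secondary 4 | corticosteroids must be stopped before Week 52 | Only for steroid use, and only in children on steroids at Baseline |

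**2. The plan's own power.** Inputs from Protocol Section 8.2 and SAP Section 4.3: p0 = 0.1837; combined doses n = 57, p1 = 0.36, two-sided 5%; high dose n = 28, p1 = 0.41, two-sided 4.95%.

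Power = Φ{[(p1 − p0)√n − z√(p0(1 − p0))] / √(p1(1 − p1))}, with √(0.1837 × 0.8163) = 0.3872.

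- Combined: (0.1763 × 7.550 − 1.960 × 0.3872) / 0.480 = 1.19, power 88.3% (stated 88%).
- High dose: (0.2263 × 5.292 − 1.964 × 0.3872) / 0.492 = 0.89, power 81.3% (stated at least 80%).

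Both stated figures reproduce.

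**3. How many remitters the tests need.** z = (x/n − p0) / √(p0(1 − p0)/n).

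| Group | x | z | p | Result |
|---|---|---|---|---|
| Combined, n = 57 | 16 | 1.89 | 0.0586 | not significant |
| | 17 | 2.23 | 0.0255 | significant |
| High dose, n = 28 | 9 | 1.88 | 0.0598 | not significant |
| | 10 | 2.37 | 0.0178 | significant |

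The planned counts are 0.36 × 57 = 20.5 and 0.41 × 28 = 11.5. Falling from 20–21 to 16 takes 4–5 recoded children; falling from 11–12 to 9 takes 2–3. One child is 1/57 = 1.8 points or 1/28 = 3.6 points. At the planned rates, the binomial chance of landing on 17–18 of 57 is 15.9%, and on 10–11 of 28 it is 28.3%. In those trials one or two children decide the test.

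**4. Illustration only.** The documents give no number of affected children. Let k be the assumed number of the 57 who are remitters only because added therapy is not scored.

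| k | Power if the planned 36% includes k and they are failed (p1 = 0.36 − k/57) | P(X ≥ 17) at rate 0.1837 + k/57 |
|---|---|---|
| 0 | 88.3% | 2.4% |
| 1 | 82.3% | 5.3% |
| 2 | 74.4% | 10.1% |
| 3 | 64.8% | 17.2% |

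The last column is a false-positive rate only if the studies behind 18.37% scored added therapy as failure. The documents do not say whether they did.

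**The case against.** **Rescue therapy means adalimumab.** Wherever the term is used descriptively, it refers to open-label adalimumab (Protocol Sections 5.1 and 5.5.1, SAP Section 4.2) or to adalimumab after a flare, as in SAP Section 9.1: "regardless of double-blind or open-label treatment or if it was rescue therapy after disease flare". Added UC drugs are treated as concomitant medication, and Protocol Section 8.1 leaves analysis detail to the SAP. On that reading the SAP simply makes the protocol rule operational. It is even stricter, because it fails children from the first blinded re-randomization. This stands as far as it goes. A reader might infer that protocol and SAP contradict each other; that is possible but not shown. The reading does not close the gap: new treatment for a flare would still be ignored on a co-primary endpoint, without a statement that this is meant.

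**Other analyses help.** MI may cover added drugs, SAP Section 10.6 permits further sensitivity analyses, ranked secondary 4 covers part of the steroid route, and UC-related concomitant medications are tabulated (SAP Section 7.3). These limit or reveal the problem. None commits the plan to scoring it.

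**The counts show small-sample fragility.** Correct: any scoring choice moves the rate by 1.8 points per child at n = 57. If children on added therapy remitted at 18.37% to 36% (an assumption), 4–5 such remitters would imply about 11 (4/0.36) to 27 (5/0.1837) of 57 children treated this way. Nothing in the documents supports that frequency. A result nearer the threshold would need fewer.

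**Re-randomization may be routine.** Section 5.5.1 words the arm-level steps as will be. Sections 5.1 and 8.3 say may, so the route remains open.

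**The benchmark is conservative.** The 18.37% is an upper 95% limit, and failing added therapy here could make the comparison less like-for-like if the placebo studies did not. The limit addresses sampling error, not scoring. The comparability point stands and is why both scorings should be shown.

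**Conclusion.** The concern holds as a gap in the confirmatory scoring rule. A Week 52 remission reached with a corticosteroid, immunosuppressant or 5-ASA added for a flare counts as an adalimumab success on co-primary 2 unless the child was also re-randomized, and no planned sensitivity analysis clearly tests this. It rests on the text of SAP Section 6.0 and on re-randomization being optional.

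A reader might infer that the co-primary test is biased in favour of adalimumab. The documents do not support that: the number of affected children is not given, the placebo studies' handling of added therapy is not described, and the benchmark is an upper limit, so the net bias is unknown. A reader might also see a second gap in the immunosuppressant paragraph of Protocol Section 5.3.1.1, which refers to loss of clinical response rather than flare. That term is undefined there, and nothing here depends on it.

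No stated power figure is wrong. The change should be made because the thresholds are 17 of 57 and 10 of 28, and a few children scored by an unstated choice can matter.

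**What to change.** - **SAP Section 6.0, NRI.** Add that a subject who, at or after Week 12, starts, re-initiates or increases over the current dose a corticosteroid, immunosuppressant or 5-ASA for worsening UC is a non-responder from that date, whether or not re-randomized.
- **Exclude** weight-based dose adjustments, resumption after an interruption for toxicity, and the return to the Baseline corticosteroid dose allowed from Week 4 to Week 12.
- **Compare with the current dose, not the Baseline dose.** Otherwise a child tapered from 40 mg to 5 mg and raised back to 40 mg for a flare at Week 20 would still count as a remitter.
- **Use one definition** for rescue therapy in Protocol Section 8.1.4 and the synopsis, and for rescue medication in the MI rule.
- **Report** the number recoded by arm, and show the unrecoded result as a sensitivity analysis.

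**Cost.** One definition, carried into the SAP and two places in the protocol. Reason for use, dose and dates are already recorded for medication received during the study (Protocol Section 5.2.3.1), so no new data are needed. Reasons for dose changes must be reviewed before database lock, and the adalimumab remission rate may be slightly lower.

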4.3 Sample Size

[figure not shown]
The co-primary endpoints will be tested first for the combined high and standard adalimumab dose groups versus external placebo and then individual dose groups versus external placebo separately, controlling the familywise Type I error (multiple significance level) of 5% in a strong sense. For each individual test the nominal power will be calculated.

Assuming a 48% remission rate per PMS at Week 8 for the combined standard and high adalimumab induction dose groups and a remission rate per PMS of 19.83% for external placebo, a total of 77 subjects (presuming HD:SD = 46:31) in ITT-E population (see Section 5.1) provides at least 99% power for a one-sample two-sided Chi-square test using a significance level of 5%.

Assuming a 36% remission rate per Mayo Score at Week 52 for the combined standard and high maintenance dose groups and a remission rate per Mayo Score of 18.37% for external placebo, a total of 57 subjects (presuming HD:SD = 28:29) in the combined adalimumab maintenance dose groups in mITT-E population (see Section 5.1) provide 88% power for a one-sample two-sided Chi-square test using a significance level of 5%.

Assuming that the high adalimumab dose regimen is associated with higher efficacy than the standard adalimumab dose regimen and assuming a 52% remission rate per PMS at Week 8 for the high adalimumab induction dose group and a remission rate per PMS of 19.83% for external placebo, 46 subjects in the high adalimumab induction dose group of ITT-E population provide at least 99% power for a one-sample two-sided Chi-square test using a significance level of 4.95%.

Assuming a 41% remission rate per Mayo Score at Week 52 for the high adalimumab maintenance dose group and a remission rate per Mayo Score of 18.37% for external placebo, a total of 28 subjects in the high adalimumab maintenance dose group of the mITT-E population provide at least 80% power for a one-sample two-sided Chi-square test using a significance level of 4.95%.

Based on the assumption of a 75% response rate at Week 8, 93 subjects were to be included in the study (presuming 12 internal placebo subjects in the maintenance part of the study who were included prior to Amendment 4) to ensure 57 subjects in the combined adalimumab maintenance dose groups.

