- a. Randomized high induction dose (I-HD): randomized prior to Protocol Amendment 4 to adalimumab 2.4 mg/kg (maximum dose of 160 mg) at Baseline and at Week 1, adalimumab 1.2 mg/kg (maximum dose of 80 mg) at Week 2, followed by a dose of 0.6 mg/kg (maximum dose of 40 mg) at Weeks 4 and 6.
- b. Randomized standard induction dose (I-SD): randomized prior to Protocol Amendment 4 to adalimumab 2.4 mg/kg (maximum dose of 160 mg) at Baseline and matching placebo at Week 1, adalimumab 1.2 mg/kg (maximum dose of 80 mg) at Week 2, followed by a dose of 0.6 mg/kg (maximum dose of 40 mg) at Weeks 4 and 6.
- c. Open-label high induction dose (I-HD-OL): enrolled under Protocol Amendment 4 or later versions with adalimumab 2.4 mg/kg (maximum dose of

[figure not shown]

160 mg) at Baseline and at Week 1, adalimumab 1.2 mg/kg (maximum dose of 80 mg) at Week 2, followed by a dose of 0.6 mg/kg (maximum dose of 40 mg) at Weeks 4 and 6.

- d. Double-blind High maintenance dose (M-HD): adalimumab 0.6 mg/kg (maximum dose of 40 mg) ew
- e. Double-blind Standard maintenance dose (M-SD): adalimumab 0.6 mg/kg (maximum dose of 40 mg) eow with matching placebo on the alternate week
- f. Double-blind Placebo (M-PL): placebo

Additionally for RR population:

- M-HD with re-induction dose (F-REIND): Subjects randomized to M-HD and (due to 1st disease flare) re-randomized to receive re-induction dose (2.4 mg/kg [maximum of 160 mg]) at the visit, then resumed to receiving the high dose (0.6 mg/kg [maximum of 40 mg]) ew.
- M-HD without re-induction dose (F-NREIND): Subjects randomized to M-HD and (due to 1st disease flare) re-randomized to maintain the high dose (0.6 mg/kg [maximum of 40 mg]) ew.
- M-SD with re-induction dose (F-REIND): Subjects randomized to M-SD and (due to 1st disease flare) re-randomized to receive re-induction dose (2.4 mg/kg [maximum of 160 mg]) at the visit, then resumed to receiving the standard dose (0.6 mg/kg [maximum of 40 mg]) eow.
- M-SD without re-induction dose (F-NREIND): Subjects randomized to M-SD and (due to 1st disease flare) re-randomized to receive one dose of 0.6 mg/kg [maximum of 40 mg] and then maintained the standard dose (0.6 mg/kg [maximum of 40 mg]) eow.
- M-PL with re-induction dose (F-REIND): Subjects randomized to M-PL and (due to 1st disease flare) re-randomized to receive re-induction dose (2.4 mg/kg [maximum of 160 mg]) at the visit. Afterwards, subjects were to receive the standard dose (0.6 mg/kg [maximum of 40 mg]) eow.

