10.6 Efficacy Sensitivity Analyses

[figure not shown]
Sensitivity analyses of the co-primary and ranked secondary endpoints based on OC, mNRI, LOCF and MI (see Section 6.0) will be conducted as applicable. Moreover, the PP population will be used for a sensitivity analysis of the co-primary and ranked secondary endpoints based on NRI.

Additional sensitivity analyses may be performed as deemed appropriate.

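### The observed-case analysis, and LOCF in effect, drops flare-rescued subjects from the Week 52 denominators instead of counting them as failures, which inflates those sensitivity rates as flares increase

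*SAP*

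**What the plan says.** Protocol 8.1.4 sets the rule for maintenance: subjects "who receive rescue therapy during the maintenance period will be considered as failures from that time point forward". In the same paragraph it prescribes NRI for binary endpoints and LOCF and OC for continuous ones.

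SAP 10.6 goes further and plans "Sensitivity analyses of the co-primary and ranked secondary endpoints based on OC, mNRI, LOCF and MI", as applicable, plus a per-protocol analysis with NRI. All of those endpoints are binary. SAP 6.0 treats flare rescue differently in each method:

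- **NRI (primary):** failure at and after the first re-randomization for flare.
- **MI:** subjects given rescue medication are set to non-response.
- **OC:** "Observed case analysis will be performed on data until 1st re-randomization of subjects with a disease flare"; missing values are not used.
- **LOCF:** the last value before or at the first re-randomization is carried forward, and baseline or earlier values may not be used.
- **mNRI:** failure only from the switch to open-label treatment at the second flare.

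Two other conventions in SAP 6.0 bear on LOCF. Endoscopy for the Mayo score is scheduled only at screening and at Week 52, or at early termination after Week 26. A Mayo score with any missing subscore is itself missing.

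**The concern.** A rescued subject is not missing in the ordinary sense, because the outcome under the protocol's rule is known. Every flare stratum in Protocol 5.1 implies a Partial Mayo Score of at least 3 at the flare visit (Week 8 score 0 plus 3 is the lowest case). Mayo remission, which needs a total of 2 or less, is therefore impossible at that visit whatever the endoscopy shows. For Mayo response and mucosal healing the score does not settle the matter, but the rescue rule does.

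Removing these subjects discards failures and keeps every remitter. Because the comparator is a fixed external rate, no control-arm rate shifts with it. The OC rate improves in proportion to how often adalimumab fails and is rescued. A reader shown OC and LOCF beside NRI could take a higher rate as support when it comes from the shrunken denominator.

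**Working it through.** **Inputs.** From SAP 4.3: n = 57 in the combined maintenance groups, null rate p0 = 0.1837, planned rate p1 = 0.36, one-sample two-sided chi-square test at 5%. The proportion re-randomized for flare, f, is not given in the documents; 10% to 40% is assumed. No other data are taken to be missing.

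**The plan's own figure.** SAP 4.3 begins: "Assuming a 36% remission rate per Mayo Score at Week 52 for the combined standard and high maintenance dose groups". Power = Φ{[(p1 − p0)√n − 1.96√(p0(1 − p0))] / √(p1(1 − p1))} = Φ{(0.1763 × 7.550 − 1.96 × 0.3872) / 0.48} = Φ(1.19) = 88.3%. The stated 88% is reproduced.

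**What each rule does to the rate.** Let x be the Week 52 remitters who were never rescued, and d the number rescued before Week 52.

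- NRI: x/57
- OC as written: x/(57 − d)
- OC with rescued subjects kept as failures: x/57 when nothing else is missing

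With all 57 retained, the smallest significant count is 17 (29.8%, p = 0.026); 16 gives p = 0.059.

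**Count needed under OC as written.**

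| Re-randomized (assumed) | OC denominator | Remitters needed | Same count under NRI | NRI p |
|---|---|---|---|---|
| 10% | 51 | 15 | 26.3% | 0.12 |
| 20% | 46 | 14 | 24.6% | 0.23 |
| 30% | 40 | 13 | 22.8% | 0.39 |
| 40% | 34 | 11 | 19.3% | 0.86 |

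For example, 12 remitters are 12/57 = 21.1% under NRI (p = 0.60). With 40% flares they become 12/34 = 35.3% under OC (p = 0.011).

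**How often OC exceeds the bar when true remission equals it.** The number rescued is binomial(57, f). Remission among those not rescued is q = 0.1837/(1 − f), so that remission overall stays at 18.37%. For each possible denominator, the exact binomial probability of reaching that denominator's critical count is taken, then averaged over the number rescued.

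| f | Expected OC rate, q | OC above the bar at p<0.05 |
|---|---|---|
| 0% (or rescued kept as failures) | 18.4% | 2.4% |
| 10% | 20.4% | 7% |
| 20% | 23.0% | 14% |
| 30% | 26.2% | 27% |
| 40% | 30.6% | 46% |

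At the planned 36% with 30% re-randomized, OC would read 0.36/0.70 = 51.4%.

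**LOCF, by combining rules.** A rescued subject may carry only a post-baseline value from before or at re-randomization. No endoscopy is scheduled in that interval. The screening endoscopy is barred, and so is the baseline composite score as a fallback. The Mayo score and endoscopy subscore therefore stay missing, and the subject drops out of Mayo remission, Mayo response and mucosal healing. An unscheduled endoscopy before or at the flare would be an exception, because LOCF admits unscheduled values. Without such endoscopies, and with nothing else missing, the LOCF denominator equals the OC denominator.

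**The case against.** **OC and LOCF are sensitivity analyses only, and drive no confirmatory decision.** This stands. The percentages above are not type I error rates of the trial; they show how easily the OC result can look positive. Adding 5% truly missing raises them to 20/36/57%, but that extra is ordinary OC behaviour and is left out here.

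**The protocol's rescue rule sits beside NRI, and OC and LOCF are assigned there to continuous endpoints.** This is also right, so the SAP does not simply break the protocol. The gap arises because the SAP extends OC and LOCF to binary endpoints without carrying the failure rule over. Sensitivity analyses may vary assumptions about missing data, but a rescued subject's status is not missing.

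**The LOCF drop-out is not written anywhere.** True. It is an inference from several rules and applies to most rescued subjects, not necessarily all.

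**A reader might infer that these checks are defective because they can never contradict the primary result.** The documents do not support that as a fault. NRI already scores every missing and rescued subject as a failure, so it is the floor against a fixed rate. Corrected OC, x/(57 − missing), still cannot fall below it, and neither can MI. The per-protocol NRI analysis can move either way.

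**A reader might also infer that mNRI undermines the primary comparison, because internal placebo subjects receive adalimumab at their first flare and can still count as successes.** They can, but SAP 5.1 excludes placebo from mITT-E, so their rate never enters the test against the external rate. In an internal contrast the credit works against adalimumab. Failing only placebo subjects at the first flare, while the adalimumab arms keep credit for remission after theirs, would be an asymmetric rule favouring adalimumab. No such change is proposed.

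**Conclusion.** The point holds for OC as written, and for LOCF by inference on the Mayo and endoscopy endpoints. Flare-rescued subjects leave the Week 52 denominators, and the resulting rate rises with the flare rate. With n = 57, true remission at 18.37% and nothing else missing, OC exceeds the bar in about 14%, 27% and 46% of trials at assumed flare proportions of 20%, 30% and 40%, against 2.4% when rescued subjects count as failures. The size depends wholly on the flare rate, which the documents do not give; the direction does not.

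The primary result is not inflated. NRI, MI and per-protocol NRI already count rescued subjects as failures. What is at stake is how far OC and LOCF can be read as corroboration.

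**What to change.** In SAP 6.0, under Observed Cases and LOCF, state that for binary endpoints a subject re-randomized for disease flare stays in the denominator as a non-responder at and after the first re-randomization. Only truly missing data are then dropped (OC) or carried forward (LOCF). Continuous endpoints can keep the present rules.

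The change needs a short addition to the text and reuses the flag already derived for NRI. The OC and LOCF rates become less favourable. The change removes the flare-driven inflation only; it does not turn OC into a stress test of NRI.
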